Infusion/Injection Site Reaction Assessment				X		X	X	X	X	X							
PK blood sampling			X		X		X	X	X	X	X	X				X	
CCI [REDACTED]																	
Banked Biospecimens for Genetics Prep D1 ^h		X															
Banked Biospecimens for Biomarkers Prep B2.5		X							X								
Sample(s) CCI [REDACTED] analyses of hormone levels: HGH, IGF-1, TSH, T4 and Cortisol ^k																	
Adverse event monitoring	X	X	→	→	→	→	→	→	→	→	→	→	→	→	→	X X	
Discharge from Clinic											X						

a. Procedures should be completed within ±10% of the collection time (ie, 2 hours ±12 minutes; 6 hours ±36 minutes, etc).

- Procedures should be completed within ±10% of the collection time (ie, 2 hours ±12 minutes; 6 hours ±36 minutes, etc).
- A full PE may be done at screening or deferred to Day -1 at the discretion of the principal investigator. A limited PE will be performed at discharge; a full PE may be performed instead, at the discretion of the Investigator. At any time during the study, a limited PE may be performed at the discretion of the investigator if there is a new or ongoing AE.
- FSH test is performed only in WONCBP at screening to confirm postmenopausal status in females who have been amenorrhoeic for at least 12 consecutive months.
- Biospecimens for exploratory cytokine analyses will be collected pre-dose (-2 hrs to -5 min), 30 minutes (±5 min) after the end of infusion, 2, 12, 24 and 48 hours after IV infusion starts. Biospecimens will be analyzed ad hoc based on clinical signs of cytokine release syndrome.
- To establish a baseline, telemetry should be recorded for at least 2 hours before dosing. This may be done immediately prior to dosing or at some 2 hour continuous interval in the 24 hours prior to dosing, as long as the recording is performed when the participant is awake. Continuous cardiac monitoring will be conducted -15 minutes pre-dose through the 8 hour post dose period.

- f. ECGs will be collected in triplicate approximately 2-4 minutes apart at pre-dose, and during clinical confinement at the times specified in the [Schedule of Activities](#) (Day 1 prior to dose to morning of Day 5, ie 96 hours post-dose). Single ECGs will be collected at all other designated visits.
- g. Vital signs include supine blood pressure, pulse rate, respiratory rate, and temperature.
- h. If not collected on the designated collection day, collect at the next available time point when biospecimens are being collected in conjunction with a participant visit.

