- i. For Cohort 1, the follow-up visit is up to Day 29 (± 3 days). For Cohorts 2 and 3, the final follow-up visit will be determined based on safety and PK data emerging from previous cohort(s), which may be earlier than Day 71 (± 3 days) but will be at least through Day 29 (± 3 days).
- j. Pregnancy test is performed only in WOCBP.
- k. Hormone samples will be collected in the morning. Beginning at baseline visit (Day -1 or predose Day 1), samples should be collected at approximately the same time in the morning.
- l. Randomization may be performed Day -1, or prior to first dose on Day 1.

Table 2. Part 1. Schedule of Activities for Multiple Ascending Doses in Healthy Participants (Cohorts 10-14)**Screening to Day 8 Visits (1st Dose)**

Visit Identifier	Screening	Clinical Confinement										Out-patient Visit	Early Termination	
		Study Day	Day-28 to Day-2	Day -1	Day 1				Day 2	Day 3	Day 4	Day 5		
Hours After Dose (for clinical confinement portion)					-2 hrs to -5 min	0	End of infusion ^{b,e}	2 ^b	6 ^b	12 ^b	24 ^b	48 ^b	72 ^b	96 ^b
Informed consent	X													
Demography, Medical history	X													
Update to medical history		X												
Physical examination ^c	X													X
Height	X													
Body Weight	X	X ^a												
History of Drug, Alcohol, and Tobacco use	X													
Inclusion/Exclusion Review	X	X ^a												
Admission to Clinical Research Unit		X												
Randomization		X ^a												
Discharge from Clinic												X		X
Laboratory (hematology, blood chemistry, urinalysis)	X	X ^a								X	X		X	X
Urine Drug Test	X	X												
Serum FSH ^d	X													
Urine pregnancy test ⁱ	X	X												X
HIV, HBsAg, HBcAb, HCVAb	X													
QuantiFERON – Tuberculosis Gold	X													
12-Lead ECG ^f	X		X		X	X	X	X	X	X	X		X	X
Vital Signs ^g	X		X		X	X	X	X	X	X	X		X	X
Prior/Concomitant Medication	X	X	X	X	X	X	X	X	X	X	X	X		X
Study Intervention Administration				X										
Infusion/Injection Site Assessment					X		X	X	X	X	X	X		
PK blood sampling				X		X	X	X	X	X	X	X	X	X
CCI														
Banked Biospecimens for Genetics Prep D1 ^h		X												

Visit Identifier	Screening	Clinical Confinement											Out-patient Visit	Early Termination	
		Day-28 to Day-2	Day -1	Day 1					Day 2	Day 3	Day 4	Day 5			
Study Day	Day-28 to Day-2	Day -1		-2 hrs to -5 min	0	End of infusion ^{b,e}	2 ^b	6 ^b	12 ^b	24 ^b	48 ^b	72 ^b	96 ^b	Day 8 ±1 day	
Hours After Dose (for clinical confinement portion)															

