- Procedures should be completed within ±10% of the collection time (ie, 2 hours ±12 minutes; 6 hours ±36 minutes, etc).
- Infusion pertains *only* to the IV cohort and does not pertain to the SC Cohorts.
- Physical examination prior to the third dose will be at the discretion of the investigator, based on any review of potential adverse events or other clinical signs/symptoms.
- ECGs will be collected in triplicate approximately 2-4 minutes apart pre-dose, and during clinical confinement at the times specified in the **Schedule of Activities** (Day 29 prior to dose and up to 48 hours post-dose). Single ECGs will be collected at all other designated visits.
- Vital signs include supine blood pressure, respiratory rate, pulse rate, and temperature.
- Pregnancy test is performed only in WOCBP.
- Hormone samples will be collected at the same time of day, in the morning.

Table 3. Part 2. Schedule of Activities in AD Participants – Cohort 9

Visit Identifier	Screening	Week 1	Week 2	Week 3	Week 4	Week 6	Week 8	Week 12	EOS Week 16	ET
Day relative to dose (Day 1)	Day-28 to Day-2	Day 1	Day 8	Day 15	Day 29	Day 43	Day 57	Day 85	Day 113	
Visit Window - Days			±3	±3	±3	±3	±3	±3	±3	
Screening Assessments										
Informed consent	X									
Demography	X									
Medical History (including AD)	X									
Height	X									
Body Weight	X	X ^a								
Drug, Alcohol and Tobacco History	X	X ^a								
FSH ^d	X									
HIV, HBsAg, HBcAb, HCVAb	X									
QuantiFERON TB Gold	X									
Inclusion/Exclusion	X	X								
Randomization		X ^a								
Laboratory Assessments										
Safety labs (hematology, blood chemistry, urinalysis)	X	X ^b	X		X	X	X	X	X	
Urine Drug Test	X	X ^a								
Pregnancy test ^d	X	X			X		X	X	X	
PK blood samples		X ^b		X	X	X	X	X	X	
CCI										
Medical Procedures										
Physical Examination ^c	X								X	X

Visit Identifier	Screening	Week 1	Week 2	Week 3	Week 4	Week 6	Week 8	Week 12	EOS Week 16	ET
Day relative to dose (Day 1)	Day-28 to Day-2	Day 1	Day 8	Day 15	Day 29	Day 43	Day 57	Day 85	Day 113	
Visit Window - Days			±3	±3	±3	±3	±3	±3	±3	
12 Lead -ECG ^f	X	X ^{b,f}	X	X	X	X	X	X	X	X
Spirometry (FEV1, FVC) ^k	X			X	X	X	X	X	X	X
Vital Signs ^g	X	X	X	X	X	X	X	X	X	X
Exploratory Biomarker										
Banked Biospecimens for Genetics Prep D1 ^h		X ^a								
Banked Biospecimen -Prep PBMC2		X ^a	X			X		X	X	X
Banked Biospecimen -Prep R1		X ^a	X			X		X	X	X
Banked Biospecimens for Biomarkers Prep B2.5		X ^a	X			X		X	X	X
Serum IgE		X ^a	X			X		X	X	X

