Serum TARC (CCL17)		X ^a	X			X		X	X	X
Plasma for Interleukin-31 (IL-31) and Interleukin-17A (IL-17A)		X ^a	X			X		X	X	X
Whole Blood for Flow Cytometry		X ^a	X			X		X	X	X
Skin Punch Biopsies -nonlesional		X								
Skin Punch Biopsies lesional		X		X		X				
Physician Assessments										
Columbia Suicide Severity Rating Scale (C-SSRS)	X									
Fitzpatrick Skin Type Assessment	X									
Eczema Area and Severity Index (EASI)	X	X ^a	X	X	X	X	X	X	X	X
CCI		█	█	█	█	█	█	█	█	█
Patient Reported Outcomes										
Pruritus Numerical Rating Scale (Pruritus NRS) ⁱ		X ^a	X	X	X	X	X	X	X	X
Dermatology Life Quality Index (DLQI)		X ^a	X	X	X	X	X	X	X	X
Patient Global Assessment (PtGA)		X ^a	X	X	X	X	X	X	X	X

Visit Identifier	Screening	Week 1	Week 2	Week 3	Week 4	Week 6	Week 8	Week 12	EOS Week 16	ET
Day relative to dose (Day 1)	Day-28 to Day-2	Day 1	Day 8	Day 15	Day 29	Day 43	Day 57	Day 85	Day 113	
Visit Window - Days			±3	±3	±3	±3	±3	±3	±3	
Patient-Oriented Eczema Measure (POEM)		X ^a	X	X	X	X	X	X	X	X
Hospital and Anxiety Depression Scale (HADS)		X ^a	X	X	X	X	X	X	X	X
ACQ-5 ^k		X ^a				X			X	X
Other Study Activities										
Contraception Check ^d	X	X	X	X	X	X	X	X	X	X
Adverse Event Monitoring	X	→	→	→	→	→	→	→	X	X
Prior/Concomitant Treatment	X	→	→	→	→	→	→	→	X	X

- a. Study procedures will be collected prior to first dose on Day 1.
- b. Day 1 will include the following: 1) pre-dose vital signs, ECG and PK CCI [REDACTED], 2) post-infusion ECG, vital signs, PK blood sample, and 3) 2 hours after the start of the infusion ECG, vital signs and blood samples for PK and cytokine release analyses.
- c. A full PE will be done at screening, or can be deferred to pre-dose on Day 1 at the discretion of the investigator. A limited PE will be conducted at all other timepoints indicated, or at the discretion of the investigator if clinically indicated.
- d. FSH test is performed only in WONCBP at screening to confirm postmenopausal status in females who have been amenorrhoeic for at least 12 consecutive months. Contraception checks and pregnancy tests will be conducted in WOCBP.
- e. Biospecimens for cytokine release labs will be collected pre-dose (-2 hrs to -5 min), 30 minutes (±5 min) after the end of infusion, and 2 hours after IV infusion starts. Biospecimens will be analyzed ad hoc based on clinical signs of cytokine release.

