3.2. Objectives, Endpoints and Estimands: Part 2 (Atopic Dermatitis Participants)

Objectives	Endpoints	Estimands
Primary:	Primary:	Primary:
To evaluate the safety and tolerability of PF-07242813 versus placebo, in participants with moderate to severe AD.	Incidence of treatment-emergent adverse events (AEs and SAEs); vital signs, safety laboratory tests, and ECG.	There is no defined estimand for these endpoints; they will be analyzed using CaPS as applicable.
Secondary:	Secondary:	Secondary:
To compare the efficacy of PF-07242813 versus placebo on percent change from baseline in Eczema Area and Severity Index (EASI) in participants with moderate to severe atopic dermatitis (AD).	Percent change from baseline in EASI total score at Week 6.	
Estimand E1: This estimand is intended to provide a population level estimate of the treatment effect of the study intervention on a continuous endpoint; without prohibited medications during treatment.
 
Study Intervention: PF-07242813 or placebo.
 
Population: Participants with moderate to severe AD as defined by the inclusion and exclusion criteria.
 
Variable: Percent change from baseline in EASI total score at Week 6.
 
Intercurrent Events:
 
a. Prohibited medications – all scores in participants who receive prohibited medication post randomization to Week 6 will be omitted from the analysis and treated as missing scores. Missing scores will be imputed based on the assumption that participants do not benefit from the study intervention.b. Inadequate compliance – participants data will be used as recorded. 
Events a and b are stated with precedence in descending order.
 
Population level summary:
 
The percent change from baseline mean difference between PF-07242813 and placebo in EASI score.

PFIZER CONFIDENTIAL

PFIZER CONFIDENTIAL

Objectives	Endpoints	Estimands
	CC1 [REDACTED]	

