7.2. Participant Discontinuation/Withdrawal From the Study

A participant may withdraw from the study at any time at his/her own request. Reasons for discontinuation from the study include the following:

- Refused further follow-up;
- Lost to follow-up;
- Death;
- Study terminated by sponsor.

At the time of discontinuing from the study, if possible, an early discontinuation visit should be conducted. See the [SoA](#) for assessments to be collected at the time of study discontinuation and follow-up and for any further evaluations that need to be completed. The early discontinuation visit applies only to participants who are enrolled/randomized and then are prematurely withdrawn from the study. Participants should be questioned regarding their reason for withdrawal.

If a participant withdraws from the study, he/she may request destruction of any remaining samples taken and not tested, and the investigator must document any such requests in the site study records and notify the sponsor accordingly.

If the participant withdraws from the study and also withdraws consent (see [Section 7.2.1](#)) for disclosure of future information, no further evaluations should be performed and no additional data should be collected. The sponsor may retain and continue to use any data collected before such withdrawal of consent.

Lack of completion of all or any of the withdrawal/early termination procedures will not be viewed as protocol deviations so long as the participant's safety was preserved.

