8.2.6. Infusion and Injection Site Reaction Assessment

Participants will be monitored for signs of any infusion or injections site reactions, including but not limited to erythema, swelling, bruising, pain or pruritus at times specified in the [SoA](#).

Any signs or symptoms related to either an infusion or injection site reaction should be treated according to the Investigator's standard of care and reported as adverse events. All anaphylactic reactions will be assessed according to Sampson's criteria.

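### Table 3 (Part 2, Cohort 9) marks no safety laboratory sample at early termination, although safety labs are part of the Part 2 primary endpoint

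*Protocol*

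**What the plan says.** Protocol 3.2 defines the Part 2 primary endpoint as "Incidence of treatment-emergent adverse events (AEs and SAEs); vital signs, safety laboratory tests, and ECG". SAP 3.2.1 specifies the laboratory component as how often abnormalities occur and how large they are.

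In Protocol 1.2, Table 3, the row "Safety labs (hematology, blood chemistry, urinalysis" has marks from Screening to Day 113 except Day 15, and none under ET. In the same ET column, marks appear for physical examination, ECG, vital signs, "Adverse Event Monitoring", IgE, TARC, IL-31/IL-17A, flow cytometry and the PBMC, R1 and B2.5 banked specimens.

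In Part 1 the corresponding row, "Laboratory (hematology, blood chemistry, urinalysis", is marked under Early Termination (Tables 1 and 2).

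Protocol 7.2 sends sites to the schedule "for assessments to be collected at the time of study discontinuation and follow-up". Section 8.2.4 likewise takes the timing of required labs from the schedule. Sections 8.2 and 8.2.4 permit unscheduled labs but do not require them.

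On the secondary point, Section 8.2.6 states "Participants will be monitored for signs of any infusion or injections site reactions, including but not limited to erythema, swelling, bruising, pain or pruritus", with timing again left to the schedule. Table 1 has a row "Infusion/Injection Site Reaction Assessment" and Table 2 has an equivalent. No such row is visible in Table 3.

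**The concern.** A site that follows the protocol literally will draw blood at a Part 2 ET visit for exploratory markers and take nothing for a component of the primary endpoint. No reason is given for Part 2 to differ from Part 1. Cohort 9 receives a single dose, so the ET visit is the last planned safety contact for someone who leaves. A laboratory abnormality arising after the last scheduled sample would not enter the count of abnormalities in SAP 3.2.1 unless someone chose to order an unscheduled test.

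The infusion-reaction point is separate. A cross-reference that leads to no time points leaves each site to decide when to look, so Part 2 would lack the timed assessment that Part 1 has.

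**Working it through.** The plan states no figure on this point, so there is none to reproduce. The check is a reading of the table followed by simple arithmetic.

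**1. Read the Table 3 rows against the ten columns** (Screening, Days 1, 8, 15, 29, 43, 57, 85, 113, ET).

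| Row | Marked at | ET |
|---|---|---|
| Safety labs | Screening, 1, 8, 29, 43, 57, 85, 113 | blank |
| Pregnancy test | Screening, 1, 29, 57, 85, 113 | blank |
| PK | 1, 15, 29, 43, 57, 85, 113 | blank |
| Physical examination | Screening, 113 | marked |
| ECG, vital signs | all visits | marked |
| Serum IgE | 1, 8, 43, 85, 113 | marked |
| AE monitoring | throughout | marked |

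Each row resolves to ten cells. The three blanks at ET all fall in the laboratory block. The physical-examination row directly below that block does carry its ET mark.

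**2. What an early leaver has.** All labs up to the last attended laboratory visit, plus AEs, ECG, vital signs and physical examination at ET. Only the exit laboratory sample is absent.

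**3. Age of the last laboratory value.** Scheduled post-screening lab days are 1, 8, 29, 43, 57, 85 and 113. The intervals are:

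8 − 1 = 7; 29 − 8 = 21; 43 − 29 = 14; 57 − 43 = 14; 85 − 57 = 28; 113 − 85 = 28.

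The longest nominal gap is 28 days. With the ±3-day window used at both ends it is 28 + 3 + 3 = 34 days. This assumes that no scheduled lab visit was missed before leaving; a missed visit would lengthen it.

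**4. How many participants.** Cohort 9 has 24 participants (Protocol 9.2.2). The early-termination rate is an assumption:

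- 5%: 24 × 0.05 = 1.2
- 10%: 24 × 0.10 = 2.4
- 20%: 24 × 0.20 = 4.8

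That is about 1 to 5 participants.

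**5. Infusion reactions.** Section 8.2.6 relies on schedule times, and Table 3 shows none. The infusion is a single Day 1 event, so any gap applies to all 24 participants and is unrelated to early termination. Table 3 footnote b does provide ECG and vital signs after the infusion and at 2 hours, and Section 8.2.6 requires reactions to be reported as adverse events.

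**The case against.** The strongest objection is that the point rests on cells in a machine-read, partly redacted table. Some Table 1 rows show merged cells at the right-hand edge. In Table 3 three neighbouring laboratory rows are all blank at ET, including "PK blood samples", which could be a shared reading fault. This justifies checking the original, but it does not defeat the point: the physical-examination row just below was read with its ET mark.

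The objection carries more weight for infusion reactions. Table 3 as read also lacks a study-drug administration row, and footnotes e and j (cytokine and hormone samples) have no visible row. A missing infusion-reaction row is therefore weak evidence that the plan omits the assessment.

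Three stronger readings are tempting, and the documents do not support them.

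- *A reader might infer that primary safety data are lost for early leavers.* Only the exit laboratory sample is missing; the other primary components are scheduled at ET and earlier labs are kept.
- *A reader might infer that the loss is selective, because people with abnormal labs are the ones who leave.* Nothing in the documents shows this. Stopping study drug is not leaving the study (Section 7.1 keeps participants for about 70 days after the last dose). Section 8.2.4 asks for clinically significant abnormal labs to be repeated until they resolve. The reasons for leaving in Section 7.2 are refusal, loss to follow-up, death and sponsor termination. Several of these yield no ET sample whatever Table 3 says.
- *A reader might infer that infusion reactions in the two parts cannot be compared.* Reactions are reportable adverse events in both parts, and safety is summarised descriptively. At most they are ascertained differently.

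**Conclusion.** The point holds in a limited form. As printed, Table 3 takes no exit sample for one component of the Part 2 primary endpoint, and no other section requires one. The consequence is a last laboratory value up to about 28 days old (about 34 with windows) for roughly 1 to 5 of 24 participants. The count rests on an assumed 5-20% early-termination rate and is a ceiling on what the fix can recover, because some leavers will not attend an ET visit. The finding also assumes that the blank ET cell is in the original table. No sample size, test or efficacy estimate is affected. This is a cheap improvement to the schedule and not a flaw in the analysis.

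The infusion-reaction point is secondary: a cross-reference to be reconciled, which concerns everyone dosed in Cohort 9.

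**What to change.** Check the original Table 3. If the ET cell is blank there, mark safety labs (hematology, chemistry, urinalysis) under ET. The cost is one more tube and a urinalysis at a visit that already draws blood, plus a schedule correction. An early leaver forgoes later draws, so the approximate 510 mL total for Cohort 9 and the limit of 550 mL per 60 days in Section 8 should not be threatened. While the table is open, confirm whether the blank ET cells for PK and pregnancy testing are intended; Section 4.2.2 describes pregnancy testing at all study visits, which Table 3 does not show.

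Separately, reconcile Section 8.2.6 with Table 3, so that the reference to schedule times for infusion-reaction monitoring either leads to entries for Cohort 9 or is reworded. This costs a text or table edit.

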2. INTRODUCTION

PF-07242813 is an anti-CD1a antibody that is being developed as a treatment for patients with moderate to severe atopic dermatitis.

2.1. Study Rationale

This is the first time PF-07242813 will be given to humans. The purpose of the study is to evaluate the safety, tolerability, and pharmacokinetics of escalating single and repeat doses of PF-07242813 in healthy participants and in participants with moderate to severe atopic dermatitis. **CCI**

2.2. Background

AD is a common inflammatory skin disease, especially in children with a prevalence of 5-20% and ~11% in the total population of the US (Oyoshi et al. 2009; Williams 2005).^{15,20} Current treatments for AD include emollients, and topical anti-inflammatory agents such as corticosteroids and calcineurin inhibitors. These agents have generally been unsatisfactory for the treatment of moderate to severe disease. More recently, an injectable monoclonal antibody directed against the IL-4 receptor α (dupilumab) that blocks the binding of IL-4 and IL-13 has been approved for the treatment of moderate to severe AD. While dupilumab represents a considerable advance in the treatment of AD, not all patients respond well or achieve completely clear skin. Moreover, some patients may become refractory to dupilumab with prolonged dosing. Additional treatments are needed that are complementary to currently approved drugs that increase the proportion of patients achieving complete resolution of skin inflammation and/or are effective in patients who do not respond or become refractory to dupilumab.

CD1a is an MHC class I-like molecule expressed on Langerhans cells in the skin. CD1a presents lipid antigens found in the skin which can be recognized by antigen-specific T cells, leading to subsequent T cell activation (de Jong et al. 2014).⁷ Emerging data suggest that pathogenic lipids, signaling through CD1a, may be important drivers of inflammation in AD (Berdyshev et al. 2018; Cooper 1994; Cully 2016; Jarrett et al. 2016; Kim et al. 2016).^{1,5,6,11,13}

PF-07242813 is a novel humanized monoclonal antibody that binds CD1a protein with high affinity and selectivity. PF-07242813 prevents CD1a from interacting with T cell receptors, leading to the inhibition of T cell activation. Therefore, PF-07242813 would be expected to inhibit T cell activation and downstream proinflammatory signaling. This mechanism would be distinct from currently available treatments that are either broadly immunosuppressive (eg, corticosteroids and calcineurin inhibitors) or specifically targeted to type 2 inflammation (eg, dupilumab).

